12.4 Physical Examination

A standard physical examination is sufficient, assessing all core body functions.

12.5 Neurological Examination, Including Toronto Clinical Neuropathy Score

A basic, manual neurological examination will include all items of TCNS:

- Muscle strength/weakness in arms and legs
- Ataxia (gait, stance and finger-nose coordination)

- Light touch (upper and lower extremity)
- Pinprick (upper and lower extremity)
- Position sense (toes and thumbs)
- Reflexes (knee and ankle)

The thresholds for “Normal=0” for all Sensory Test Scores are set as follows: Subject can discriminate any of these qualities (pinprick, temperature, light touch, vibration, position sense) at least at the secondary (more proximal) region to test that quality (see **Error! Reference source not found. Table 3** for primary and secondary skin-areas).

Table 3 Primary and Secondary Skin Area to Test the Sensory Quality

Sensory quality	Distal (primary) area	Proximal (secondary) area
1. Pinprick	Plantar area of foot	Ankle
2. Temperature	Plantar area of foot	None
3. Light touch	Plantar area of foot	Ankle
4. Vibration	Medial malleolus	Patella
5. Position	Big toe	Thumb

12.6 Vital Signs

The following vital signs will be recorded during this study (this must include but not be limited to the measurement of orthostatic changes in heart rate and blood pressure):

- Heart rate (beats per minute [bpm])
- Blood pressure (supine, according to Riva-Rocci’s method, plus orthostatic change in blood pressure; pathologic orthostatic changes are defined as: Decrease of ≥ 15 mmHg diastolic last supine to first standing or decrease ≥ 20 mmHg systolic last supine to first standing or increase of pulse ≥ 20 bpm)
- Body temperature (Celsius or Fahrenheit)
- Height (Baseline only; feet or cm)
- Weight (pounds or kg)

12.7 Nerve Function Monitoring

NFM consists of sensory testing (vibration and thermal perception), motor and sensory nerve neurography (amplitude and conduction velocity) and clinician-rated outcome in TCNS. Subject-related outcome measure, NTSS-6, is part of NFM, and is discussed in [Section 12.8](#). The aim is to detect intra-subject worsening from before treatment as an indicator for neurotoxicity. Subject total “Before Treatment” status is calculated as the average of the Screening visit and Baseline visit data. The tests will follow existing local standards and procedures, but should be run in a consistent fashion within a given site and subject to minimise intra-subject variability, e.g. constant skin temperature of the feet of at least

32°C/90°F, same assessor, same procedures, same chronological order of assessments, same time of day. Measurements will be taken twice for each assessed nerve in both the left and right extremity. The NFM can be conducted \pm 3 days of the scheduled protocol visit, except at the Baseline visit, where it must be conducted within 3 days prior to the randomisation step.

The following tests will be performed:

- Vibration detection threshold: Note that vibration is also part of the TCNS. This test will be performed with a Rydel–Seiffer graded tuning fork (64 Hz, 8/8 scale) that is placed over a bony prominence (medial malleolus) of each foot and left there until the subject can no longer feel any vibration. Threshold will be determined as a disappearance threshold with two stimuli repetitions of each foot.

Subjects with the ability to define a threshold within two assessments (even if at 1/8) will be graded “Normal=0” in TCNS. If the subject cannot discriminate such a threshold at the medial malleolus (most distal point to measure), the same exercise will be repeated with the tuning fork placed over the patella.

- Thermal (cold and warm) detection (qualitative) at both legs, at the lateral mid-dorsum of the feet; using the Minnesota Thermal Discs with Copper (C; felt as colder) and polyvinyl (P; felt as warmer than copper) at room temperature. Sites open to enrolment under this amendment that do not have access to Minnesota Thermal Discs, will continue to conduct thermal detection via cold and warm vials, as per the following: Thermal (cold and warm) detection (qualitative) at both legs, using one vial filled with ice water and one filled with warm water. This assessment will also be included in the scoring of TCNS. The subject will be asked (with eyes closed) whether it feels warm or cold when one of these vials is touching his/her feet. The number of correct answers out of 10 attempts (five with warm and five with cold in a random order) will define the threshold. Where subjects have less than five correct answers, the same test will be repeated in an area in the middle of the lower leg, up to the knee. If the subject can detect at least 6/10 correctly, the subject will be scored “0” (normal) in TCNS.

This assessment will also be included in the scoring of TCNS. Each disc is placed in random order for about 2 seconds over the lateral dorsum of each foot. The subject will be asked (with eyes closed) whether a disc feels warmer or colder (relative to each other). The two discs will be positioned in random order (C then P; or P then C) 10 times at each foot. After testing the first foot, the same procedure will be performed on the other side.

1. If 9 or 10 pair tests at each side are identified correctly: the subject is eligible.
2. If 8 or less pairs are correctly named as “warmer” or “colder” at any foot: exclude the subject.

If the subject can detect at least 9 of /10 pairs correctly, the subject will be scored “0” (normal) in TCNS.

- Nerve conduction: Local equipment, procedures and normal values will be used. The measures will be obtained twice for each assessed nerve. For the second measure, all

electrodes need to be placed again. Preferably, surface electrodes will be used. It is recommended to measure in the following order: Sural No 1 – Peroneal No 1 – Sural No 2 – Peroneal No 2, to ensure independent measures.

- Sensory - Sural nerve: In case the Sural nerve is not measurable for SNAP, the Ulnar nerve or Median nerve will be used for sensory neurography as “back-up” nerves. SNAP amplitude will be assessed Baseline-to-peak. The number of repetitions will be according to local standards. NCV will be calculated according to local standards.
- Motor - Peroneal nerve: Only if the Peroneal nerve is not measurable for CMAP, the Tibial nerve motor component will be used as back-up. CMAP amplitude will be measured peak-to-peak. The number of repetitions will be according to local standards. NCV will be calculated according to local standards.

The NFM should follow existing local standards and procedures and should be run in a consistent fashion. Please see [Table 4](#) for a summary of the NFM assessments and personnel involved:

Table 4 NFM Requirements

Outcome	Test	Conducted by	Frequency	Protocol reference
Clinician-rated	Toronto Clinical Neuropathy Score (TCNS)	Certified neurologist or a physician who has received appropriate training from a neurologist	Every visit, except ad hoc or unscheduled safety visits, i.e. maximum 6 times	Section 12.5
Sensory testing	Vibration detection threshold			Section 12.7
	Thermal detection			
Neurography	Motor and sensory nerve (amplitude and conduction velocity)	Individual trained in these techniques, which may include (but is not limited to) a neurologist, neurophysiologist or neurophysiology assistant		
Subject-rated	Neuropathy Total Symptom Score-6 (NTSS-6)	Health care professional, e.g. study nurse, study coordinator	Every visit, including ad hoc and unscheduled safety visits, i.e. approximately 6 times	Sections 12.7 and 12.8

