 - a) Inability to sense a stimulus even at the secondary (more proximal) skin area for pinprick, light touch, and vibration or temperature at the foot, in at least one extremity (in case neurography measures are normal, the case will be discussed with the ICON MM to assess subject eligibility)
 - b) Nerve conduction abnormalities beyond local normal values or inability to measure SNAP or CMAP in the primary or a secondary (back-up) nerve
 - c) NTSS-6 score > 6, but note that subjects are eligible even if they show:
 - Missing reflexes of the Achilles tendon (ankle), but a positive patellar (knee) tendon reflex
 - Missing ability to name toe or thumb position
6. Has had a stroke within the year prior to randomisation, as determined by the investigator.
7. Has a lifetime diagnosis of a major psychiatric disorder (other than dementia), based on the Diagnostic and Statistical Manual of Mental Disorders, 4th Edition criteria. This

- includes but is not limited to schizophrenia, schizoaffective disorder, bipolar affective disorder, alcohol dependence syndrome or major depressive disorder.
8. Has a history of disease directly related to the hypothalamus, the pituitary and/or the adrenal glands which affect the hypothalamic-pituitary-adrenal axis function.
 9. Has uncontrolled clinical conditions relating to glucose and lipid metabolism.
 10. Clinically significant ECG abnormalities, including QTc interval > 450 msec, following ECG tracings at Screening. A single repeat evaluation will be allowed if the investigator or designee has reason to believe the reading is faulty or to help assess the clinical significance of an abnormality. Any other ECG abnormality that is seen as exclusionary will first be discussed with the ICON MM.
 11. Use of any prohibited medication (see [Section 10.8](#) for details).
 12. Participation in another clinical study of an investigational drug or device whereby the last drug/device administration is within 60 days of Screening.
 13. Inability to communicate well with the investigator (i.e. language problem, non-fluent English [as scales will be provided in English only], poor mental development or impaired cerebral function).
 14. Subject will undergo the tests, ADAS-Cog v14, CDR-SOB, MMSE, NTB (executive domain) and RAVLT at the indicated time-points to avoid uncontrolled learning effects. Subjects who need to perform these tests externally to and in parallel with this study will be excluded.

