Once the above assessments have been performed, the following can be performed in the order most convenient to the investigator/study site staff:

7. Physical examination (including height and weight), neurological examination and vital signs measurement (blood pressure, heart rate, respiration rate and oral temperature). The neurological examination shall cover all aspects of the TCNS:

- Muscle strength/weakness in arms and legs
- Ataxia (gait, stance and finger-nose coordination)
- Light touch (upper and lower extremity)
- Pinprick (upper and lower extremity)
- Position sense (toes and thumbs)
- Reflexes (knee and ankle)

The thresholds for “Normal=0” for all Sensory Test Scores are set as follows: Subject can discriminate any of these qualities (pinprick, temperature, light touch, vibration, position sense) at least at the secondary (more proximal) region to test that quality (see [Table 3](#) for primary and secondary skin-areas).

8. NTSS-6 (subject and caregiver): The six questions of NTSS-6 should be completed as part of the assessment of subjects’ medical history, also asking for input from the caregiver to make sure no information is lost. Each item will also be graded for its frequency and intensity, adding up to a total score from “0” to “21.96” points. A total score of > 6 would exclude the subject from the study.

9. NFM: for details see [Section 12.7](#). Two measures for each test will be obtained and averaged. The test must be undertaken and reviewed by suitably qualified and experienced personnel. The following tests will be performed:

- Vibration detection threshold
- Thermal (cold and warm) detection
- Nerve conduction (velocity and amplitude)
 - Sensory nerve - Sural nerve or back-up nerves (Ulnar nerve or Median nerve) SNAP and NCV
 - Motor nerve - Peroneal nerve or back-up nerve (Tibial nerve) CMAP and NCV

For quality control measures, the results of neurography of one subject per study site will be reviewed by a member of the DSMB Nerve Function Monitoring sub-committee. The

study site will complete a Neurography Screening Quality Control Form and send it to the ICON MM ([contact]). The study site may, however, proceed with subject randomisation if all eligibility criteria are fulfilled.

10. Laboratory sampling:

- A blood sample will be taken for haematology and biochemistry, pregnancy test (WOCBP only) and Vitamin B12. If there is clinical concern about a female subject's menopausal status, FSH will be measured.

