 7. NFM: for details see [Section 12.7](#). Perform the assessment at the area the subject could detect the sensory stimulus during the Screening visit. Two measures for each test will be obtained and averaged. Both extremities will be assessed. The test must be undertaken and reviewed by suitably qualified and experienced personnel. The NFM can be conducted within 3 days prior to the scheduled protocol visit, but must be prior to the randomisation step. Even in case Screening and Baseline are scheduled within 1 week, a second NFM assessment is required.

Example: Subject was able to detect a vibration threshold at the medial malleolus at 2/8, perform the vibration threshold testing again at the medial malleolus. Where subjects can no longer detect vibration at the medial malleolus (but at patella with a threshold of 4/8), this would still reflect a worsening and may disqualify the subject from further participation.

The following tests will be performed:

- Vibration detection threshold
- Thermal (cold and warm) detection
- Nerve conduction (velocity and amplitude)

- Sensory nerve - Sural nerve or back-up nerves (Ulnar nerve or Median nerve) SNAP and NCV
- Motor nerve - Peroneal nerve or back-up nerve (Tibial nerve) CMAP and NCV

If any of these NFM tests show a deterioration from the “Before Treatment” status (calculated as the average of the Screening visit and Baseline visit data), please contact the ICON MM ([contact]) within 24 hours of becoming aware of the deterioration, to define follow-up activities and assess whether the subject must be withdrawn from study.

8. Randomise the subject visit using ICON IWRS, dispense study drug and provide the subject with a Subject Visit-by-Visit Guide (which also contains the Drug Intake Diary).

Note: the first dose of study drug must be taken in the presence of the investigator/study site staff, to ensure compliance, and enable the subject to open the drug container and make an entry into the Drug Intake Diary.

9. Assess AEs.
10. Complete scales (MMSE [subject only] and CDR-SOB [subject and caregiver]).
11. Neuropsychological scales (ADAS-Cog v14 [subject only], RAVLT [subject only], NTB [subject only], and NPI [caregiver only]):
 - The neuropsychological testing should be performed during the same period of the day at the Screening, Baseline (Week 0) and EOT (Week 12) visits to minimise a confounding impact of fluctuations in vigilance.

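### The vial test for the TCNS temperature item can turn 4/10 at the foot into normal but not 5/10; its lower-leg repeat contradicts Table 3, and the SAP does not separate vial from disc results

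*Protocol*

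**What the plan says.** Protocol 12.7 allows two thermal tests. Sites with Minnesota Thermal Discs use those; sites without them continue with vials of warm and ice water, five attempts of each in random order.

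- **Vials, retest:** "Where subjects have less than five correct answers, the same test will be repeated in an area in the middle of the lower leg".
- **Vials, pass mark:** "If the subject can detect at least 6/10 correctly, the subject will be scored" 0 on the TCNS. This sentence comes directly after the retest sentence and names no body area.
- **Discs, pass mark:** "If the subject can detect at least 9 of /10 pairs correctly, the subject will be scored" 0. Eight or fewer at either foot excludes the subject. No proximal repeat is given.

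Protocol 12.5 defines a normal sensory score as follows: "Subject can discriminate any of these qualities (pinprick, temperature, light touch, vibration, position sense) at least at the secondary (more proximal) region". Protocol 9.4.1.1 has the same sentence. Table 3, directly below it in 12.5, enters None as the proximal area for temperature. Exclusion criterion 5a (Protocol 9.3.2) speaks of "vibration or temperature at the foot, in at least one extremity".

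SAP 7.8.4.2 scores each sensory test 0 or 1, abnormal if either side is abnormal. It sums all items to a total of 0 to 19 and counts abnormal sensory results by treatment group and overall. It does not mention vials, discs or test site.

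**The concern.** A retest rule should not treat a better result worse. Here 4/10 gets a second chance at an easier site and 5/10 does not. With five warm and five cold attempts, 5/10 is exactly the score of a subject who gives the same answer every time.

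The repeat also matters for what the monitoring is for. Protocol 12.7 says: "The aim is to detect intra-subject worsening from before treatment as an indicator for neurotoxicity". If a pass at the lower leg makes the item normal, a foot that cannot tell warm from cold can stay at 0. The documents point both ways on whether it does: Table 3 says there is no proximal area, the sentence above Table 3 lists temperature among the qualities that may pass proximally, and 12.7 does not say which area the 6/10 refers to. Two assessors could score the same findings differently.

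Finally, a TCNS temperature abnormality means fewer than 6 of 10 at a vial site and fewer than 9 of 10 at a disc site. The SAP plans no thermal summary outside the TCNS, so nothing in the planned output would show the difference.

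**Working it through.** **The plan's own NFM figure.** Protocol 15.1 gives about 90% probability of seeing at least one event of true rate 3% among 78 subjects, and over 98% at 5%. 1 − 0.97^78 = 0.907 and 1 − 0.95^78 = 0.982, so both reproduce. The present point does not depend on them.

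**Mapping the vial scores (Protocol 12.7).**

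| Foot score | Retest at leg | TCNS item |
|---|---|---|
| 6 to 10 | no | 0 |
| 5 | no | 1 by default (binary item, pass mark not met) |
| 0 to 4 | yes | 0 or 1, depending on whether a leg pass counts |

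**Inputs.** Ten attempts, retest below 5, pass at 6 or more, disc pass at 9 or more: all from 12.7. Protocol 9.4.1.1 and SAP 7.8.4 add "Two measures for each test will be obtained and averaged", so each result is given for one set of ten and for two sets averaged (20 attempts; pass at 12 or more in total, retest below 10). The documents give no per-attempt accuracy, so every accuracy below is an assumption.

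**Foot at chance, independent coin-flip answers.**

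| Quantity | One set, Bin(10, 0.5) | Two sets, Bin(20, 0.5) |
|---|---|---|
| Vial pass | P(X ≥ 6) = 37.7% | P(X ≥ 12) = 25.2% |
| Retest | P(X < 5) = 37.7% | P(X < 10) = 41.2% |
| Gap: no pass, no retest | P(X = 5) = 24.6% | P(10 ≤ X ≤ 11) = 33.6% |
| Disc pass | P(X ≥ 9) = 1.07% | P(X ≥ 18) = 0.02% |

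If the lower leg is intact and a leg pass counts, the chance of a normal score on one side is pass plus retest: 0.3770 + 0.3770 = 75.4%, or 0.2517 + 0.4119 = 66.4%. The item is abnormal if either side is, so both sides must pass: 0.7539² = 56.8% or 0.6636² = 44.0% with the repeat, against 0.3770² = 14.2% or 0.2517² = 6.3% without it.

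**Sensitivity to how people guess.** A subject who always gives the same answer scores 5/10 every time: 100% in the gap, 0% passing. A guesser who gives five of each answer can score only even numbers: in one set 0% fall in the gap and 50% pass. The coin-flip gap figures are therefore single points in a range from 0% to 100%.

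**Who is affected by a foot-only rule.** The event is a foot score below 6/10 on either foot at Screening or Baseline (2 feet × 2 visits, taken as independent).

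- Accuracy 0.90, one set: P(X < 6) = 0.00163; 1 − (1 − 0.00163)^4 = 0.65%.
- Accuracy 0.80, one set: P(X < 6) = 0.0328; 1 − (1 − 0.0328)^4 = 12.5%.
- Two sets averaged: 0.02% at 0.90 and 3.9% at 0.80.

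**The case against.** **A reader might infer that 5/10 has no score at all.** The documents do not support this. SAP 7.8.4.2 makes the item binary and 12.7 requires at least 6/10 for normal, so 5/10 is abnormal by default. What stands is the mismatch between a retest trigger below 5 and a pass mark of 6.

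**A reader might infer that the repeat plainly breaks exclusion 5a.** That holds only if the words about the foot limit temperature to the foot. The criterion opens by referring to the secondary skin area, so another reading is possible, and it sends cases with normal neurography to the medical monitor. The contradiction with Table 3 needs no such reading.

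**The proximal pass may be intended.** The secondary-region sentence and 12.7 both point that way, vibration likewise moves to the patella, and entering the lower leg in Table 3 would also restore consistency. This is a fair alternative. On its own, though, it would leave 4/10 treated better than 5/10, and it would keep a proximal route for vials that discs do not have.

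**The consequences are small.** Randomisation is in blocks stratified by site (Protocol 10.2.4), and 12.7 asks for the same procedures within site and subject. Any observed NFM worsening is reported under 12.7.1. For vibration, Protocol 9.4.1.2 says of a shift to the more proximal site that "this would still reflect a worsening and may disqualify the subject from further participation". All of this stands and limits the harm. It does not say which area decides the temperature score.

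**A mid-study rule change could create apparent worsening** in subjects scored under the old rule at Screening and Baseline. This stands, and the fix must deal with it.

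**Conclusion.** The point holds as a minor defect in a stated rule. The vial retest trigger and pass mark do not fit together, and the lower-leg repeat contradicts Table 3. The SAP mixes two definitions of normal, by silence and not by declaration.

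The effect is on sensitivity and interpretability. Under coin-flip answering at the foot, an intact leg and a leg pass that counts, the repeat moves the chance of a normal item (both sides) from 14.2% to 56.8% with one set, or from 6.3% to 44.0% with two sets averaged. These figures depend on response style and apply only to subjects with no thermal discrimination at the feet.

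A reader might go further and suspect a biased treatment comparison. The site-stratified randomisation makes that unlikely, and no efficacy result or stopping boundary uses this item. The number of vial sites is not stated, so the effect on the pooled counts cannot be sized.

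**What to change.** 1. **Protocol 12.7, TCNS scoring of the vial test.** The foot result decides: at least 6/10 is 0, anything lower is 1. A lower-leg result may be recorded but does not change the score.
2. **Protocol 9.4.1.1 and 12.5.** Remove temperature from the secondary-region sentence so that it agrees with Table 3.
3. **Subjects already enrolled.** Derive the item from the recorded foot result at every visit, including Screening and Baseline, so that the change creates no apparent worsening. This requires that the foot result was recorded separately.
4. **Eligibility.** Leave criterion 5a and its medical monitor route as they are.
5. **SAP 7.8.4.2.** Show the temperature item and the count of abnormal sensory results by thermal method used at the visit, as well as pooled.

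The cost is a few wording edits and one extra table split. If the method is not in the database, it can be taken from the site's equipment record. The subjects who would score 1 on the item before treatment are the 0.65% (accuracy 0.90) or 12.5% (0.80) from the working with one set, or 0.02% and 3.9% with two sets averaged. Many of them already score 1 under the default reading. The vial pass mark and the sample size do not change.

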 8. NFM - for details see [Section 12.7](#). Perform the assessment at the area the subject could detect the sensory stimulus during the Baseline visit. Two measures for each test will be obtained and averaged. Both extremities will be assessed. The test must be undertaken and reviewed by suitably qualified and experienced personnel. The NFM can be conducted \pm 3 days of the scheduled protocol visit. The following tests will be performed:
 - Vibration detection threshold
 - Thermal (cold and warm) detection
 - Nerve conduction (velocity and amplitude)
 - Sensory nerve - Sural nerve or back-up nerves (Ulnar nerve or Median nerve) SNAP and NCV
 - Motor nerve - Peroneal nerve or back-up nerve (Tibial nerve) CMAP and NCV

If any of these NFM tests show a deterioration from the “Before Treatment” status (calculated as the average of the Screening visit and Baseline visit data), please contact ICON MM ([contact]) to define follow-up activities and assess whether the subject must be withdrawn from study.

9. Record AEs. AEs of special interest (AESIs) (worsening of NFM [calculated as the average of the Screening visit and Baseline visit data] or prolongation of QTc) must be treated as SAEs and notified to ICON Pharmacovigilance (PV) within 24 hours (see [Section 12.1.1](#)). ICON PV or ICON MM will then contact the study site to explain the required next steps for further evaluation.
10. Perform study drug accountability and review Drug Intake Diary for completion compliance.
11. Schedule the second Interim (Week 8) visit.
12. Remind the subject to document the time of study drug intake on each day and to attend the Interim (Week 8) visit in a fasted state.
13. Remind the caregiver that he/she is required to be present at all visits (but not for all scales).
14. Before leaving the study site, the second PK sample (3 to 5 hours post-dose; as described in No. 1 above), should be drawn.

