8. NFM - for details see [Section 12.7](#). Perform the assessment at the area the subject could detect the sensory stimulus during the Week 4 visit. Two measures for each test will be obtained and averaged. Both extremities will be assessed. The test must be undertaken and reviewed by suitably qualified and experienced personnel. The NFM can be conducted \pm 3 days of the scheduled protocol visit. The following tests will be performed:
 - Vibration detection threshold
 - Thermal (cold and warm) detection
 - Nerve conduction (velocity and amplitude)
 - Sensory nerve - Sural nerve or back-up nerves (Ulnar nerve or Median nerve) SNAP and NCV
 - Motor nerve - Peroneal nerve or back-up nerve (Tibial nerve) CMAP and NCV

If any of these NFM tests show a deterioration from the “Before Treatment” status (calculated as the average of the Screening visit and Baseline visit data), please contact ICON MM ([contact]) to define follow-up activities and assess whether the subject must be withdrawn from study.

9. Record AEs. AESIs (worsening of NFM [calculated as the average of the Screening visit and Baseline visit data] or prolongation of QTc) must be treated as SAEs and notified to ICON PV within 24 hours (see [Section 12.1.1](#)). ICON PV or ICON MM will then contact the study site to explain the required next steps for further evaluation.
10. Perform study drug accountability and review Drug Intake Diary for completion compliance.

11. Schedule the EOT (Week 12) visit.
12. Remind the subject to document the time of study drug intake on each day and to attend the EOT (Week 12) visit in a fasted state.
13. Remind the caregiver that he/she is required to be present at all visits (but not for all scales).
14. Before leaving the study site, the second PK sample (3 to 5 hours post-dose; as described in No. 1 above), should be drawn.

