7.8.4.3 Neurography (SNAP, CMAP and NCV)

Neurography (nerve conduction velocity and amplitude) of peripheral sensory and motor nerves will be tested. Measurements will be taken twice for each assessed nerve in both the left and right extremity. Two measures for each test will be obtained and averaged. Descriptive statistics for absolute value and absolute change from Baseline for neurography (SNAP, CMAP and NCV – sensory nerve and motor nerve assessment) data will be presented for screening, Baseline (Week 0), Interim (Week 4), Interim (Week 8), EOT (Week 12), Follow-up (4 weeks post last dose of study drug) by treatment group and overall. Neurography data will be listed.

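### Back-up nerves and proximal re-testing on treatment let the per-arm nerve-function tables understate a lost distal response

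*Protocol*

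**What the plan says.** The purpose of nerve function monitoring (NFM) is stated in Protocol 12.7: "The aim is to detect intra-subject worsening from before treatment as an indicator for neurotoxicity".

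**Neurography.** The sensory rule in 12.7 is "In case the Sural nerve is not measurable for SNAP, the Ulnar nerve or Median nerve will be used for sensory neurography". The motor rule is "Only if the Peroneal nerve is not measurable for CMAP, the Tibial nerve motor component will be used as back-up". Neither is limited to a visit. The Week 4 list (9.4.1.3) reads "Sensory nerve - Sural nerve or back-up nerves (Ulnar nerve or Median nerve) SNAP and NCV", and the same item stands in the Week 8, EOT and Follow-up lists. SAP 7.8.4.3 plans "Descriptive statistics for absolute value and absolute change from Baseline for neurography", covering SNAP, CMAP and NCV as a sensory and a motor assessment. It names no nerve and has no rule for a switched nerve or an absent response. SAP 8.0 does not replace missing safety values.

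**Sensory testing.** Protocol 12.5 scores a sensory item Normal=0 if the subject can discriminate the quality "at least at the secondary (more proximal) region to test that quality". Under 12.7, vibration testing moves to the patella if no threshold is found at the malleolus. SAP 7.8.4.2 codes each sensory item 0 or 1. The test area follows the preceding visit, for example at Week 8: "Perform the assessment at the area the subject could detect the sensory stimulus during the Week 4 visit". Yet when 9.4.1.2 describes loss at the malleolus with detection at the patella, it says "this would still reflect a worsening and may disqualify the subject from further participation".

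**Reporting.** The visit lists and 12.7.1 have the site compare with Before Treatment status (the Screening and Baseline average) and inform the medical monitor of any deterioration.

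**The concern.** A change score means something only if the same thing is measured at both times. If the Sural response is recordable before treatment and lost later, the rule supplies an arm-nerve value, and nothing in the SAP stops that value being set against the earlier leg-nerve value. The motor switch stays in the leg but raises the same problem.

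Sensory testing has a parallel weakness: a loss that moves up the limb leaves the binary item at 0. Both errors run in one direction, because a lost distal response is represented by a reading from a nerve or area that still works. At stake is the comparison between arms in the tables meant to show whether the drug affects peripheral nerves.

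**Working it through.** **1. The plan's own NFM figures (Protocol 15.1).** With n = 78 per group, the chance of at least one affected subject is 1 − (1 − p)^78.

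- p = 3%: 1 − 0.97^78 = 90.7% (stated: about 90%).
- p = 5%: 1 − 0.95^78 = 98.2% (stated: above 98%).

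Both reproduce. They concern seeing at least one case, not a mean change.

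**2. One subject with a lost response.** Let A be the pre-treatment amplitude and rA the back-up amplitude, and take a lost response as amplitude 0. The true change is (0 − A)/A = −100%. If the back-up value is used, the recorded change is (rA − A)/A = (r − 1) × 100%. The documents give no value for r, so the range is assumed.

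| r | True change | Recorded change |
|---|---|---|
| 0.5 | −100% | −50% |
| 1 | −100% | 0% |
| 1.5 | −100% | +50% |
| 2 | −100% | +100% |

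Any r above 0 understates the loss. No change or improvement needs r of 1 or more.

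If only one side is lost and a table used the mean of two equal sides, the true change is −50% and the recorded change is (r − 1)/2 × 100%: −25%, 0% or +50% at r = 0.5, 1 or 2.

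**3. A group mean.** At the protocol's 5% rate, 0.05 × 78 = 3.9, so about 4 subjects. Assume these 4 start at the group mean and the other 74 do not change.

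- True mean change: −100% × 4/78 = −5.1%.
- Recorded with back-up values: (r − 1) × 100% × 4/78 = −2.6%, 0%, +2.6% or +5.1% at r = 0.5, 1, 1.5 or 2.
- Recorded if the lost responses are left missing: 0%, from the remaining 74.

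The last line shows that removing the back-up value is not enough. The loss must also be counted.

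**4. Sensory items, passages side by side.** Protocol Table 3 gives a secondary area for four of the five qualities (pinprick, light touch, vibration, position) and none for temperature. For those four, distal loss with proximal detection changes the item by 0 − 0 = 0. For temperature, 12.7 lets sites using vials repeat the test on the lower leg, which conflicts with Table 3. Sites using thermal discs have no proximal repeat, so the problem does not arise there.

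In the 9.4.1.2 vibration example, 2/8 at the malleolus becomes 4/8 at the patella: the number rises while the text calls it a worsening. SAP 7.8.4 has analysis subsections for NTSS-6, TCNS and neurography only. No table of vibration or thermal change, or of the area tested, would recover the shift.

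**The case against.** The strongest reply is that detecting a case does not depend on the substituted number. The tester turns to the back-up only after finding the primary nerve unmeasurable. On-treatment findings are judged against Before Treatment status, not the last visit. Deterioration goes to the medical monitor, and potential signals go to two neurophysiology experts with unblinded data. Worsening that qualifies is an AESI (Protocol 12.1.1) and is tabulated by arm (SAP 7.8.1). This stands, and it limits the point. A reader might infer that nerve toxicity would go unseen; the documents do not support that. The protection is partial, though. Section 12.7.1 escalates only when two or more related parameters are affected with nothing else to explain it. AESI tables by preferred term also do not show how many subjects per arm lost a response.

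Second, the SAP never instructs anyone to pool nerves, and it lists the data. That is true: the defect is silence, not an instruction. But the stated unit is the sensory or motor assessment, and a programmer needs a rule.

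Third, the back-up may be meant for entry only, since exclusion criterion 5b mentions it, and 12.7 asks for consistency within a subject. That reading is plausible, but the option is written into every on-treatment list, and the general request does not say what to do when the original nerve fails.

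Fourth, TCNS is a coarse score and vibration is a separate test. That also stands, but the separate test then needs its own table.

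**Conclusion.** The point holds for the per-arm safety tables. As written, neurography change can compare different nerves and understate a lost response, and the TCNS tables can show no change where 9.4.1.2 describes a worsening. The size per affected subject is (r − 1) × 100% in place of −100%, with r unknown and a lost response taken as zero amplitude. How often this would happen cannot be derived from the documents.

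Two stronger readings are not supported. A reader might infer that a lost response will appear as stability or improvement; that needs r of at least 1, which the documents do not establish. A reader might also infer that the 90% and 98% figures fail. They would fall only if some share m of true events were never recognised: at a 3% rate, 1 − (1 − 0.03(1 − m))^78 is about 83% for m = 25% and 69% for m = 50%. No value of m can be drawn from the documents, and individual reporting works against it. The sample size statement is not shown to be wrong.

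**What to change.** **SAP 7.8.4.2 and 7.8.4.3**

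- Compute neurography change only within the same nerve and side as before treatment, and summarise by named nerve.
- Do not use a back-up value as the change for a lost primary nerve.
- Add per-arm counts of subjects with (a) a primary-nerve response recordable before treatment and not recordable later, and (b) a distal-to-proximal shift in any sensory quality compared with Before Treatment status.

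**Protocol 12.5, 12.7 and the visit lists**

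- Record the nerve and skin area used at each visit, and keep any back-up value as additional data.
- Reconcile the Normal=0 and back-up wording with 9.4.1.2 and 12.7.1, and Table 3 with the vial procedure for temperature.

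The tables should not decide whether every unmeasurable response is an NFM worsening. Section 12.7.1 has a category for artefacts, and NFM findings feed AESI reporting and the withdrawal criteria in 9.5. How such losses enter those rules is for the sponsor to reconcile.

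The cost is a little programming, possibly one eCRF field if nerve and area are not already captured, and a few more worsenings shown in the tables. No new procedure is needed.
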